Title of the study: Evaluation of Buccal Bone Thickness, Ridge Dimensions, And Root Position In Anterior Maxilla For Immediate Implant Placement

NCT ID: not yet assigned

ID: EU2020/470

Study Protocol CBCT (cone-beam computed tomography) images obtained for various diagnostic purposes from at least 200 individuals who met the inclusion criteria and were admitted to the Department of Oral and Maxillofacial Radiology at the Faculty of Dentistry, Erciyes University, between January 2015 and January 2020, will be included in the study. In the CBCT scans, the maxillary right and left central, lateral, and canine regions in the anterior maxilla will be evaluated. A reference line drawn through the midpoints of the teeth, parallel to their long axes, will be used to assess the morphology of the anterior crest. For each of the maxillary central, lateral, and canine teeth, alveolar crest width and height, buccal bone thickness, and root position (defined as the angle between the long axis of the root and the long axis of the alveolar crest) will be measured separately. To determine buccal bone thickness, measurements will be taken from the buccal crest apex, as well as at 1 mm, 2 mm, 4 mm, and 6 mm apical to the crest, and at the level of the tooth apex. Alveolar crest height will be defined as the distance between the nasal floor and the alveolar crest along a line drawn parallel to the long axis of the crest. Alveolar crest width will be calculated by averaging the measurements taken from the midpoints of three equal segments of the crest. The buccal undercut will be defined as the closest point between the buccal bone surface and the root in the sagittal plane, and its distance from the crest apex will be recorded. Additionally, the angle between the tooth root and the alveolar crest will be measured to determine root position in the radial plane. The distribution of these measurements will also be analyzed according to age and gender. For this purpose, CBCT images will be grouped into the following age categories: 20–29, 30–39, 40–49, 50–59, 60–69, and 70–80 years. All measurements will be performed by a single experienced professional. The statistical analysis of the data will be carried out using the SPSS (Statistical Package for the Social Sciences) software. The Kolmogorov-Smirnov test will be used to evaluate the normality of the data distribution. For comparisons between groups, One-Way ANOVA followed by Tukey's post-hoc test will be used for normally distributed variables, while the Kruskal-Wallis test will be used for non-normally distributed variables. Correlations between age, gender, and the measurements of alveolar height and width will be analyzed using Spearman's correlation coefficient.

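### The plan gives no rule for choosing the 200 or more eligible archive scans, no balance over age band and gender, and only one-factor tests, so the age comparison may be biased, weak in the oldest band, or confounded by gender

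*Combined protocol and SAP*

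**What the plan says.** The combined protocol and SAP is one section, Study Protocol, so any selection rule would have to appear there.

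- **Source.** The scans are "images obtained for various diagnostic purposes" in one radiology department, dated "between January 2015 and January 2020, will be included in the study".
- **Number.** The only figure is a floor: "at least 200 individuals who met the inclusion criteria". No ceiling, stopping point or derivation is given.
- **Age and gender.** These analyses are planned: "The distribution of these measurements will also be analyzed according to age and gender". For them, "CBCT images will be grouped into the following age categories": "20–29, 30–39, 40–49, 50–59, 60–69, and 70–80 years". No minimum or target is set for any band or for either gender.
- **Analysis.** "For comparisons between groups, One-Way ANOVA followed by Tukey's post-hoc test will be used for normally distributed variables". Kruskal-Wallis is the non-normal alternative, and Spearman's coefficient relates age and gender to alveolar height and width. No two-factor, partial or regression analysis is named.

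**The concern.** The images already exist, so which eligible ones enter is the investigator's choice. The criteria, the department and the dates define who is eligible. They do not say whether all, consecutive, random or hand-picked scans are read, or when reading stops. Three things follow.

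1. **Selection.** An unstated choice with an open upper limit allows bias, and this affects the overall description of the measurements as well as the age comparison.
2. **Precision.** Age bands are formed after the scans are chosen. The 70–80 band needs anterior teeth still present, so it may be very small, and any contrast with it would then say little.
3. **Confounding.** If the share of men differs by band and the measurement differs by gender, a one-way age comparison absorbs part of the gender difference, and the reverse. None of the named methods removes this.

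**Working it through.** **The plan's own figure.** The 200 comes with no alpha, power, SD or effect size, so it can be neither reproduced nor refuted. The documents give no age or gender distribution either. Everything below is illustrative.

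**Inputs.** From the plan: 200 individuals (the floor), six bands, one-way ANOVA with Tukey. Assumed: two-sided alpha 0.05, SD = 1, one value per individual, and three splits over the bands from youngest to oldest:
- balanced: 200/6, about 33 each
- moderate skew: 50/50/40/30/20/10
- strong skew: 60/50/40/30/15/5

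**Precision, oldest v youngest.** Half-width = (q/√2) × √(1/n₁ + 1/n₂), with q(0.05; 6, 194) = 4.071, so q/√2 = 2.878.
- 33 v 33: 2.878 × √(1/33 + 1/33) = 0.71 SD
- 50 v 10: 2.878 × √(1/50 + 1/10) = 1.00 SD
- 60 v 5: 2.878 × √(1/60 + 1/5) = 1.34 SD

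**Omnibus power, oldest band shifted by 0.7 SD.** F test on 5 and 194 df, noncentrality λ = 0.7² × n_old × (200 − n_old)/200.
- n_old = 33.3: λ = 0.49 × 33.3 × 166.7/200 = 13.6; power 81%
- n_old = 10: λ = 0.49 × 10 × 190/200 = 4.66; power 33%
- n_old = 5: λ = 0.49 × 5 × 195/200 = 2.39; power 18%

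**Linear age pattern totalling 0.8 SD from youngest to oldest.**

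| Split | 5-df omnibus F | 1-df trend test |
|---|---|---|
| Balanced | 85% | 97% |
| Moderate skew | 72% | 91% |
| Strong skew | 65% | 87% |

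The 1-df column is a parametric approximation to the planned Spearman analysis, which covers alveolar height and width only.

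**If the archive itself is short.** Suppose only 5 eligible scans exist in the oldest band. Balancing the rest gives roughly 34/34/34/34/59/5 if the shortfall is filled from the adjacent decade. λ depends only on n_old, so it stays at 2.39 and power stays at 18%. The oldest v youngest half-width is 2.878 × √(1/34 + 1/5) = 1.38 SD, no better than 1.34.

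**Confounding.** Spurious age difference = gender effect × difference in the share of men.
- Gender effect 0.5 SD, 70% v 40% men: 0.5 × 0.30 = 0.15 SD
- Gender effect 0.3 to 0.8 SD, share moving from 40% to 60%: 0.06 to 0.16 SD
- Gender effect 0.3 to 0.8 SD, share moving from 30% to 80%: 0.15 to 0.40 SD

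The type I error of the unadjusted one-way ANOVA was simulated with no true age effect and gender effects of 0.5 and 0.8 SD (3,000 runs per setting):
- no drift in gender share: about 5%
- 40% to 60% drift: 5 to 8%
- 30% to 80% drift: 12% and 25% with equal bands; 8% and 15% with the strong skew

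**Cost of equal allocation.** With equal strata weighted back to archive shares w, the design effect is 6 × Σw².
- Moderate skew: 6 × (0.25² + 0.25² + 0.20² + 0.15² + 0.10² + 0.05²) = 1.20; effective n about 200/1.20 = 167
- Strong skew: 6 × (0.30² + 0.25² + 0.20² + 0.15² + 0.075² + 0.025²) = 1.33; effective n about 151

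**The case against.** The strongest reply is that balancing may not help where help is most needed. If older patients with anterior teeth are scarce in the archive, a stratified draw cannot create them, and power for the oldest band stays at 18% with 5 scans. Topping up from the next decade does not enlarge the short band and can leave the genders unbalanced. This stands: a reader might infer that stratified sampling cures every weakness at the same total, but the documents give no archive counts to support that.

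Other points also stand in part:

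- The planned Spearman analysis loses little for a steady age trend in height and width. It does not cover buccal bone thickness or root angle, and it does not adjust for gender.
- The confounding needs both a gender effect and a gender mix that changes with age. Under mild drift it is small: 0.15 SD is well inside even the balanced half-width of 0.71 SD.
- The age and gender analysis is introduced as an addition to the main description, and equal allocation costs precision on overall means.
- The floor of 200 may be exceeded, and the inclusion sentence could be read as taking eligible scans generally. If so, saying that all eligible scans are taken would close the selection gap without quotas. The text does not settle this.

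A reader might also infer that any scans at all may be used. That goes too far: inclusion criteria, one department and a date window apply. What is missing is the rule for choosing among eligible scans.

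**Conclusion.** The concern holds. The plan commits to a six-band age comparison and a gender analysis, but leaves open which eligible scans are read, how many fall in each band, and how age and gender are separated. This is more than a missing detail, because a random draw stratified by age and gender is a better design for about the same number of readings.

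The size depends on unseen archive counts. Under the assumed splits, the main loss is in contrasts with the oldest band: a half-width of 1.00 to 1.34 SD instead of 0.71, and omnibus power of 33% or 18% instead of 81%. That loss is recoverable only if the archive holds roughly 33 eligible scans aged 70–80. The loss for a 1-df age trend is modest. Confounding by gender is a possibility that no planned analysis would remove; it is slight under mild drift and material only under strong drift. The documents do not show that imbalance or confounding will occur, only that nothing prevents or corrects it.

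**What to change.** Before any scan is selected, add a paragraph to the Study Protocol that does the following.

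1. List all eligible scans from January 2015 to January 2020 by age band and gender.
2. Draw at random within the 12 age-by-gender strata, aiming for roughly equal numbers (12 × 17 = 204 in total) and taking every scan in a short stratum. If reading all eligible scans is feasible, say so and do that instead.
3. Report eligible and selected counts per stratum.
4. Analyse age and gender together, by two-way ANOVA or regression, instead of relying on one-way tests. This is the direct remedy for confounding and is needed whichever selection rule is used.
5. Weight the strata by their eligible counts when giving overall means.
6. If the oldest stratum stays short, report its limited precision or merge it with the adjacent band, deciding from the counts before measurements are seen.

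The cost is one paragraph, an archive listing and essentially no extra readings for the stratified draw; reading all eligible scans would take more. The downside is that weighted overall means lose some precision (design effect about 1.2 to 1.33 under the assumed mixes), and a short oldest stratum remains short.

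### The buccal undercut is defined as the point where root and buccal surface are closest, which need not be an undercut and can be the crest margin

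*Combined protocol and SAP*

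**What the plan says.** The Study Protocol section is a single block of text, and it gives the undercut one sentence: "The buccal undercut will be defined as the closest point between the buccal bone surface and the root in the sagittal plane", followed by "and its distance from the crest apex will be recorded". It sets no concavity or depth criterion, no range of levels to search, and no rule for a tooth without an undercut.

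Three other statements bear on this:

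- Buccal bone thickness is read at six levels, of which the first is the crest apex itself and the last is the root tip. The crest margin is therefore inside the zone being measured.
- Root inclination is a variable of its own: "root position (defined as the angle between the long axis of the root and the long axis of the alveolar crest".
- After all the measurements have been described, the plan adds: "The distribution of these measurements will also be analyzed according to age and gender". The undercut distance comes before this sentence and is covered by it.

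**The concern.** An undercut is a feature of one curve, the outer buccal surface. The rule minimises a distance between two curves, surface and root, so its answer depends on where the root lies as well as on the contour. The two points can coincide but need not. Four consequences follow.

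1. With no search range, the crest margin (about 0 mm) is an admissible answer wherever a concavity lies.
2. Two finite curves always have a closest point, so a flat or convex ridge also receives an undercut distance.
3. With the outer contour unchanged, the recorded level moves with root inclination and taper.
4. A concavity well apical to the root tip is missed.

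The recorded distances would then mix true concavity levels, crest-margin values and values from teeth with no undercut. An age or gender difference in them could reflect how often the rule returns the crest, or how roots are inclined, and not where undercuts lie.

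**Working it through.** The plan states no figure on this point, so there is none to reproduce. That every tooth gets a value, and that the crest is admissible, follows from the wording. The geometry below shows how easily the rule departs from the concavity. **All shapes and fractions are assumptions, not patient data.**

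**Model 1: one contour, varying root lean.** Let z be mm apical to the crest.

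- Outer surface: x(z) = −D·exp(−0.5·((z − c)/2)²), a concavity of depth D centred at level c.
- Root: a straight buccal face from z = 0 to 12 mm, starting 1.5 mm inside the surface at the crest (2.0 mm for D = 1.5), leaning θ degrees palatally.
- Recorded level: the surface z at which the Euclidean distance to the root face is smallest.

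For D = 1.0 mm and c = 8 mm:

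| Palatal lean θ (degrees) | Recorded level (mm) |
|---|---|
| 0 | 8.00 |
| 6 | 7.57 |
| 7 | 7.49 |
| 8 | 0.00 |

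Crest gaps of 2 and 3 mm give the same levels.

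A hand check explains the jump. The lean adds about c·tan θ to the gap at the concavity, and the concavity removes D. The crest becomes the closest point once c·tan θ is about D, so θ ≈ arctan(1.0/8) = 7.1 degrees. The numerical search puts it at 7.4, because the minimum drifts coronally before it jumps.

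Lean at which the recorded level switches to the crest (0.05 mm or less), in degrees, to within 0.1:

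| Depth D (mm) | c = 6 mm | c = 8 mm | c = 10 mm |
|---|---|---|---|
| 0.5 | 5.0 | 3.7 | 2.9 |
| 1.0 | 10.2 | 7.4 | 5.8 |
| 1.5 | 15.5 | 11.2 | 8.8 |

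Two limiting cases:

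- No concavity (D = 0): the rule returns 0.00 mm at 1 degree of palatal lean and 12.00 mm at 1 degree of buccal lean.
- Concavity at 15 mm, beyond the 12 mm root, with θ = 0: recorded at 12.17 mm (D = 0.5) or 12.30 mm (D = 1.0).

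**Model 2: tapering root, different contours.** The root's buccal face is at 3.0 − 0.18s, where s is mm apical to the crest, over 12 mm.

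| Outer contour | Concavity? | Recorded level (mm) |
|---|---|---|
| Straight, 3.5 − 0.10s | No | 0.05 |
| Convex, 3.5 − 0.02s − 0.004s² | No | 0.01 |
| Straight, converging on the root tip, 4.2 − 0.27s | No | 12.00 |
| 3.8 − 0.10s − 1.0·exp(−((s − 8)/1.5)²) | Yes, 8 mm | 7.91 |
| 3.4 − 0.08s − 0.8·exp(−((s − 9)/1.2)²), thin crest | Yes, 9 mm | 0.03 |

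The rule finds one of the two true concavities, returns the crest for the other, and gives a value to all three profiles that have none.

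**Effect on a group comparison.** Suppose the true level is 8 mm in every tooth of both groups, and the rule returns the crest (0 mm) in a fraction p. The group mean is 8·(1 − p).

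- p = 10% versus 20%: 8 × 0.90 = 7.2 mm and 8 × 0.80 = 6.4 mm, a spurious difference of 0.8 mm.
- p = 20% versus 40%: 8 × 0.80 = 6.4 mm and 8 × 0.60 = 4.8 mm, a spurious difference of 1.6 mm.

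**The case against.** **The undercut is ancillary.** It is not in the study title or in the opening list of measurements, and the planned correlations with age and gender name only crest height and width. This limits the weight of the point. It does not remove it, because the distance is recorded and falls under the analysis by age and gender.

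**The definition is explicit and the quantity coherent.** The level at which root and buccal surface are closest is a sensible thing to measure for immediate implant placement, so perhaps only the label is wrong. That is a fair reading, and renaming is one of the two remedies offered. Under the present label, readers would take the results as undercut location.

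**An experienced reader would apply the rule only where an undercut exists.** Possibly, but no such condition is written. A single reader applying an unwritten criterion could not be checked or reproduced.

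**The magnitudes are hypothetical.** This stands. The group differences need the crest-return fraction to vary by age or gender, and the document gives no evidence either way. The modelled lean is that of the root face against the outer surface, not the plan's angle between root and crest axes, so the switching angles cannot be read against planned root-position data.

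**Crest returns would be visible.** Values near 0 mm could be spotted and compared with the thickness measurements. That would flag the problem but would not recover the level of the true concavity.

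**Conclusion.** The concern holds. Followed as written, the rule locates the thinnest buccal bone, can return the crest margin, and assigns an undercut distance to a plate that has no undercut. These statements follow from the definition and need no assumption beyond the ordinary meaning of undercut.

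The size of the effect rests wholly on assumed geometry. For concavities 0.5 to 1.5 mm deep at 6 to 10 mm, the recorded level jumps to the crest at 2.9 to 15.5 degrees of lean. Any resulting difference between groups depends on fractions that the document does not give. In some anatomies the rule does find the concavity. The defect is confined to the undercut variable and its comparisons by age and gender; buccal bone thickness, ridge dimensions and root angle are untouched. It should be corrected before the measurements are made.

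**What to change.** Define the undercut on the outer buccal contour. One option is the point of greatest perpendicular distance from a tangent line joining the most prominent coronal and apical points of the buccal surface. State how far apically the contour is followed and the minimum depth that counts as a concavity, so that absence is defined in practice. Record the distance from the crest apex where a concavity exists, and no undercut otherwise. By tooth type, age group and gender, report both the proportion of teeth with an undercut and its level among those teeth.

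If the sponsor prefers to keep the closest root-to-surface point, report it as the level of minimum buccal bone thickness and draw no conclusion from it about undercuts.

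The first option rewords one definition and uses the same scans and reader. It adds one line per slice, over at least 200 × 6 = 1,200 tooth sites if all six anterior teeth are measurable in each individual. Teeth without an undercut leave the distance analysis and are reported as a proportion. Renaming requires no additional measurement.

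### Each person supplies up to six teeth but only independent-samples tests are named; any comparison of tooth types needs a within-person method and a rule for the two sides

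*Combined protocol and SAP*

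**What the plan says.** The document is one unnumbered Study Protocol section. The sample is "at least 200 individuals who met the inclusion criteria". On each scan, "the maxillary right and left central, lateral, and canine regions in the anterior maxilla will be evaluated", so a person with a full set of anterior teeth contributes six: three types, two sides. The outcomes are laid out by tooth type: "For each of the maxillary central, lateral, and canine teeth, alveolar crest width and height, buccal bone thickness, and root position" are each to be measured separately.

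Age and gender come in afterwards: "The distribution of these measurements will also be analyzed according to age and gender". For age, "CBCT images will be grouped into the following age categories: 20–29, 30–39, 40–49, 50–59, 60–69, and 70–80 years".

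The testing rule opens with "For comparisons between groups, One-Way ANOVA followed by" and names Tukey's test as the follow-up when a variable is judged normal. For the remaining variables the plan adds "while the Kruskal-Wallis test will be used for non-normally distributed variables". The factor that forms the groups is not named. No paired, repeated-measures, Friedman, mixed-model or cluster-adjusted method appears. Nothing says whether the two sides are averaged, one is chosen, or both are entered. The only other inferential method is a Spearman correlation of age and gender with alveolar height and width.

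**The concern.** Tooth type is the main axis along which the measurements are organised, and where bone is thin is a natural question for immediate implant placement. An analyst who compares central, lateral and canine teeth under this plan has only tests built for groups of different people. The values being compared come from the same people, so the independent-groups standard error ignores the covariance between them.

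Two things are at stake. If the standard error used is too large, real differences between tooth positions can be missed. If it is too small, differences are declared too often. Which of these applies depends on how the two sides enter the analysis, and the plan does not say.

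**Working it through.** **Inputs.** From the document: at least 200 people, three tooth types, two sides, and One-Way ANOVA or Kruskal-Wallis. It gives no alpha, SD, effect size or correlation, so there is no stated figure to reproduce. Assumed: two-sided alpha 0.05, equal SDs, right-left correlation *rc* within a type, and correlation *rb* between types in the same person (the same across sides). Type I error comes from simulation with n = 200 and 2,000 replicates per scenario. The Monte Carlo standard error at 5% is √(0.05 × 0.95 / 2000) ≈ 0.5 percentage points.

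**Layout A: one value per type per person.** The variance of a difference between two type means is 2σ²(1 − rb)/n. The independent-groups test uses 2σ²/n. The ratio of true to assumed standard error is √(1 − rb):

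- rb = 0.3: √0.7 = 0.84, ANOVA type I error 1.3%
- rb = 0.5: √0.5 = 0.71, type I error 0.2%
- rb = 0.7: √0.3 = 0.55, type I error 0.0%

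If the one value is the average of the two sides, the correlation between averages is 2rb/(1 + rc). The ratio becomes √(1 − 2rb/(1 + rc)), which is below 1 for any positive rb.

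**Layout B: both sides entered as separate observations.** Each type has 2n values, so the test uses 2σ²/(2n) = σ²/n. A person's two-side mean has variance σ²(1 + rc)/2, and two such means have covariance rb σ². The true variance of the difference is (2/n)[σ²(1 + rc)/2 − rb σ²] = (σ²/n)(1 + rc − 2rb). The ratio of standard errors is √(1 + rc − 2rb): below 1 if rb > rc/2, above 1 if rb < rc/2.

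| rc | rb | SE ratio, both sides entered | Type I error, ANOVA | Type I error, Kruskal-Wallis | SE ratio, sides averaged |
|---|---|---|---|---|---|
| 0.3 | 0.3 | 0.84 | 1.1% | 1.3% | 0.73 |
| 0.5 | 0.5 | 0.71 | 0.3% | 0.3% | 0.58 |
| 0.8 | 0.5 | 0.89 | 2.8% | 2.9% | 0.67 |
| 0.8 | 0.4 | 1.00 | 5.3% | 5.9% | 0.75 |
| 0.8 | 0.3 | 1.10 | 7.9% | 9.0% | 0.82 |
| 0.7 | 0.2 | 1.14 | 10.3% | 10.5% | 0.87 |

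**Power.** One type was shifted by 0.2 SD (assumed). Repeated-measures ANOVA on side means was compared with one-way ANOVA on all six teeth:

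- rc = rb = 0.3: 94% against 86%
- rc = rb = 0.5: 99% against 91%
- rc = 0.8, rb = 0.6: 97% against 87%
- rc = 0.8, rb = 0.4: 84% against 85%, so no gain
- rc = 0.8, rb = 0.3: 76% against 83%
- rc = 0.7, rb = 0.2: 73% against 82%

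In the last two scenarios the one-way test's higher figure comes with the inflated type I error in the table.

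**Age groups, as a check on the remedy.** If all six teeth were pooled as independent observations across six equal age bands, the variance inflation is 1 + rc + 4rb. This runs from 2.5 to 4.5 over the non-zero correlations tried, with type I error of about 49% to 79%. Confining One-Way ANOVA to age and gender is therefore not enough without also fixing one value per person.

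**The case against.** The strongest objection is that no sentence commits to testing tooth types. Measuring each type separately fits descriptive results by tooth, or a separate analysis per tooth. The only groups the document defines are age bands, which are made of different people, and independent-samples tests suit those if each person gives one value. This stands. A reader might infer that the plan sets One-Way ANOVA to compare tooth types. The layout makes that plausible, especially as age and gender are introduced as additions, but the text does not say it.

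A reader might also infer that the standard error would always be too wide and power always lost. The documents do not support that either. They give no rule for the sides and no correlations, and with both sides entered the error can vanish (rc = 0.8, rb = 0.4) or reverse. The effect size is an assumption too, and the plan mentions no confidence intervals, so the direct effect is on the p-values.

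Nor do the documents show that the age and gender comparisons are invalid. The 49% to 79% figure applies only if teeth are pooled, and the plan does not say they will be.

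None of this supplies a suitable test for tooth types. Each person contributes all three, and neither named test allows for it.

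**Conclusion.** The point holds conditionally. If the undefined groups include tooth type, the named tests use a wrong standard error except where rb happens to equal rc/2 with both sides entered, or where values within a person are uncorrelated.

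The direction is settled only for one value per type per person with positive correlation. The tests are then too conservative, with the true standard error roughly half to five-sixths of the one used over assumed correlations of 0.7 to 0.3. With both sides entered, the type I error ranged from well under 1% to about 10% over the assumed correlations. Every size given here rests on assumed correlations, equal SDs and an assumed alpha; only the design facts and the minimum of 200 people come from the document.

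If no test between tooth types is intended, the plan should say so, and the point then reduces to stating the unit of analysis for age and gender.

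**What to change.** Define the groups and the unit of analysis, and add three statements to the statistical text:

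1. Any comparison of tooth types uses a within-person method. One option is repeated-measures ANOVA, or Friedman, with paired post-hoc comparisons on one value per type per person (sides averaged). The other is a linear mixed model with tooth type as a fixed effect and a random effect for person.
2. How right and left enter. If both sides go into the mixed model, add a person-by-tooth-type random effect, so that two teeth of the same type may correlate more than teeth of different types.
3. One-Way ANOVA with Tukey and Kruskal-Wallis are reserved for age and gender groups, run per tooth type with one value per person.

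The cost is a few sentences and slightly more analysis work, with no new data. Friedman drops people who lack a tooth type; the mixed model keeps them, which is a reason to prefer it if missing teeth are common.

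### For alveolar height and width, the only method named for gender is a pairwise Spearman coefficient, which gives no difference or interval in mm, and no named test takes age and gender together

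*Combined protocol and SAP*

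**What the plan says.** All of this stands in the single unnumbered Study Protocol section.

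- Aim: "The distribution of these measurements will also be analyzed according to age and gender". No method is attached to this sentence.
- Grouping: the next sentence gives age bands only, "CBCT images will be grouped into the following age categories: 20–29, 30–39, 40–49, 50–59, 60–69, and 70–80 years". Gender is not listed as a grouping.
- Group comparisons: "For comparisons between groups, One-Way ANOVA followed by Tukey's post-hoc test will be used for normally distributed variables", and "the Kruskal-Wallis test will be used for non-normally distributed variables". Which groups are meant is not stated.
- Gender and a named method together: "Correlations between age, gender, and the measurements of alveolar height and width will be analyzed using Spearman's correlation coefficient".

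The section names no confidence interval, and no regression, two-factor, stratified or partial-correlation analysis. It plans for at least 200 people and gives no expected gender mix, SD or age trend.

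**The concern.** Height is defined as a distance and width as an average of linear measurements, and the study is meant to inform implant placement. A reader who wants to know how men and women differ needs a difference in mm and a statement of its precision. Spearman's coefficient supplies neither: it does not change when the measurements are rescaled, and an interval for it would be on the correlation scale.

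The second part is that an ordinary Spearman coefficient is pairwise, and One-Way ANOVA and Kruskal-Wallis each take one factor. The last sentence lists age and gender side by side but adjusts neither for the other. It can be read as including the age-gender correlation; that could reveal an imbalance but would not remove its effect. If the gender mix changed across the age bands and the measurement changed with age, part of the unadjusted gender difference would be an age difference, and the reader could not tell how much.

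**Working it through.** The plan has no figure of its own to reproduce here. The only input from the document is 200 people (its stated minimum) and the six age bands. Gender mix, SD and age trend are assumptions, shown as ranges. The unit mm for height and width is also assumed, since the plan states it only for the buccal measurement levels.

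**1. Is Spearman with a two-category variable valid?** Yes. With gender coded as two values, (n − 1) × rho² equals the Kruskal-Wallis statistic H. In a simulated set of 200 people, 199 × rho² and H both came to 12.604.

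**2. Does the coefficient fix the size in mm?** No. In one simulated data set (100 per gender), rho was 0.252 at every scale, while the mean difference was 0.50, 1.00, 1.50 and 2.00 mm for SDs of 1, 2, 3 and 4 mm.

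The same follows from theory for normal data, where p is the share of one gender and d the difference in SD units: rho = √(3p(1 − p)) × (2·AUC − 1), with AUC = Φ(d/√2). Solving for rho = 0.20:

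| Gender mix | d (SD) | SD 1 mm | SD 2 mm | SD 3 mm |
|---|---|---|---|---|
| 50:50 | 0.415 | 0.42 mm | 0.83 mm | 1.25 mm |
| 70:30 | 0.454 | 0.45 mm | 0.91 mm | 1.36 mm |

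With untied measurements, rho for gender also cannot reach 1: its maximum is 0.87 at 50:50 and 0.79 at 70:30. It is therefore not on the same footing as the age coefficient beside it.

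**3. What precision would a difference in mm have?** With one value per person and no age trend, the half-width is 1.96 × √(1/(200p) + 1/(200(1 − p))) SD:

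- 50:50: 0.277 SD
- 60:40: 0.283 SD
- 70:30: 0.302 SD

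At 50:50 that is ±0.28, ±0.55 and ±0.83 mm for SDs of 1, 2 and 3 mm.

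**4. How much could age enter the gender difference?** Assume equal numbers in the six bands, ages at the band midpoints (24.5, 34.5, 44.5, 54.5, 64.5, 75; SD 17.2 years), 50:50 overall, a linear shift in female share across the bands, and residual SD = 1. With age slope b per year:

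- age contribution = b × gap, where gap is the male minus female mean age;
- unadjusted standard error = √(1 + b²V) × √(1/100 + 1/100), where V is the age variance within gender;
- adjusted standard error = √(1/100 + 1/100) × 1/√(1 − r²), where r is the age-gender correlation.

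| Female share, youngest to oldest band | Gap (years) | V | Size of r | Age contribution at 0.2 SD per decade | Same, in standard errors | Adjusted / unadjusted width, no trend | Same, 0.2 SD per decade |
|---|---|---|---|---|---|---|---|
| 50% to 50% | 0 | 295.9 | 0 | 0 | 0 | 1.000 | 0.946 |
| 60% to 40% | 4.70 | 290.3 | 0.137 | 0.094 SD | 0.63 | 1.010 | 0.956 |
| 70% to 30% | 9.40 | 273.8 | 0.273 | 0.188 SD | 1.26 | 1.040 | 0.987 |

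Bottom row in full: b = 0.02 per year, so the contribution is 0.02 × 9.40 = 0.188 SD. The unadjusted standard error is √(1 + 0.0004 × 273.8) × 0.1414 = 1.0533 × 0.1414 = 0.149 SD, and 0.188 / 0.149 = 1.26. The width ratio with the trend is 1.040 / 1.0533 = 0.987. With no age trend the contribution is zero in every row.

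Adjustment has two opposing effects on the width: correlation between age and gender widens the interval, and the variance that age explains narrows it.

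**The case against.** **Gender may already be one of the groups.** The aim covers all the measurements by age and gender, and the group-comparison rule is unrestricted. One-way ANOVA and Kruskal-Wallis both work with two groups, and age may be the only variable listed because only age needs cut-points. On that reading, summaries in mm by gender would follow and Spearman would be an addition. This stands as a plausible reading. Against it, a Tukey post-hoc step has a purpose only with three or more groups, and the text never says. Even on this reading, no interval is named and each test still takes one factor.

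**Nothing is shown to be invalid.** This stands. A reader might infer that correlating a two-category variable by ranks is an error; step 1 of the working shows that it is not. The unadjusted male-female difference is also a legitimate target for a descriptive study, and the coefficient need not be removed.

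**The confounding is hypothetical.** This stands too. A reader might infer that the planned gender results will be distorted by age. The document gives no gender mix, SD or age trend, so it supports no such claim. The upper figure needs a steady 70% to 30% shift in female share, equal bands and 0.2 SD per decade, all at once.

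**The mm ranges come from assumed SDs.** True. They show only that rho does not determine the size, not what the size will be.

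**Conclusion.** The point holds as a minor, nearly free improvement. For height and width, the plan commits gender by name only to a coefficient that cannot be turned into a difference in mm, leaves open whether gender also enters the group comparisons, and names no analysis with age and gender together. Confidence is high on the absence of a named mm difference, interval and two-factor analysis. It is moderate that the group comparisons do not already cover gender, and low that an age-gender imbalance will occur.

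Under the assumptions above, the unadjusted 95% CI is about ±0.28 residual SD at 50:50 with no age trend. Age would add between 0 and about 1.3 standard errors to the unadjusted difference. Adjustment would change the interval from about 5% narrower (equal mix, 0.2 SD per decade) to 4% wider (70% to 30% shift, no trend). Adjustment is therefore cheap in precision whether or not it proves necessary. The documents do not support the stronger readings that the gender analysis is wrong, that gender receives nothing but Spearman, or that its results will be confounded.

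**What to change.** For height and width, add a difference in mm with its interval, show the adjusted result beside the unadjusted one, and say whether gender is among the groups compared. Suggested wording:

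> For alveolar crest height and width, the male-female mean difference in mm will be reported with its 95% confidence interval, both unadjusted and from a linear model containing age and gender. If several teeth per person are analysed, both intervals will use robust standard errors clustered by person. The number of people in each age band will be tabulated by gender. Spearman coefficients will be reported as supplementary results.

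A random effect for person would serve in place of clustered errors. Whichever is chosen should be written down before the data are analysed, and not selected after looking at the residuals. The adjusted figures belong beside the descriptive summaries, not in place of them. Extending the model to the other measurements is optional.

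Cost: a few sentences of analysis text and one count table. Age and gender are already part of the planned analysis, so no new data are needed.
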